9.4. Statistical Analyses

The SAP will be developed and finalized before database lock and unblinding, and will describe the participant populations to be included in the analyses, along with procedures for accounting for missing, unused, and spurious data. This section is a summary of the planned statistical analyses of the primary and exploratory endpoints.

9.4.1. Efficacy Analyses

9.4.1.1. Primary Efficacy Endpoints

The efficacy endpoint is the achievement of $a \ge 2$ -grade improvement from baseline on the FWS according to investigator assessments of GL severity at maximum frown at any postintervention timepoint through Day 7.

9.4.1.2. Primary Efficacy Analyses

The purpose of the primary analyses is to test for the primary endpoint, that is, the achievement of $a \ge 2$ -grade improvement in FWS according to investigator assessments of GL severity at maximum frown from Day 1 through Day 7 for each cohort. Safety will be assessed by the DMC.

- The purpose of the primary analyses will be to test for the primary endpoint (ie, at least a 2-grade improvement response from investigator) during any timepoint after study intervention administration through Day 7 for each AGN-151586 intervention dose group versus placebo group for each cohort. For example, if it is determined by the investigator-rated FWS that participants have at least a 2-grade improvement at any postintervention assessment through Day 7, they will meet the responder definition for each assessment timepoint this applies.
- The proportion of responders for the primary endpoint for each AGN-151586 study intervention group versus placebo will be analyzed using CMH tests stratified by baseline GL severity at maximum frown, using observed data without imputation or adjustment for multiplicity. In addition, 2-sided 95% CIs for the treatment differences in response rates will be provided. Between group comparisons will only be performed for each AGN-151586 group against the placebo group. Nominal p-values will be presented for each statistical test.
- Observed data without imputation will be used with stratification based on baseline GL severity for the primary analysis described above. In addition, sensitivity analyses of the primary efficacy variable will be performed to establish consistency and robustness and further characterize the extent of participants' responses (eg, missing as nonresponder). In addition, placebo groups across cohorts can be pooled to compare with each AGN-151586 group as a supportive analysis. Details will be provided in the SAP.

AGN-151586

Baseline and posttreatment values will be summarized using descriptive statistics for the AGN-151586 dose groups and placebo group for each cohort at each assessment timepoint. Details will be provided in the SAP.

The safety analysis will be performed using the safety population and will be defined in the SAP. The safety parameters will include:

- Incidence of adverse events, including adverse event severity and causality as assessed by the investigator
- Change from baseline and values over time in clinical laboratory tests, physical examinations, vital signs, and ECGs

9.4.2.1. Adverse Events

An adverse event will be considered a TEAE if:

- The adverse event began on or after the date and time of the study intervention; or
- The adverse event was present before the date and time of the study intervention, but increased in severity or became serious on or after the date and time of the study intervention.

An adverse event that occurs after the End-of-Study Visit (Day 42) will not be counted as a TEAE.

An adverse event will be considered a TESAE if it is a TEAE that additionally meets any SAE criteria.

The number and percentage of participants reporting TEAEs in each study intervention group will be tabulated by system organ class and preferred term and by system organ class, preferred term, and severity.

The number and percentage of participants reporting treatment-related TEAEs in each study intervention group will be tabulated by system organ class and preferred term.

If more than 1 adverse event is coded to the same preferred term for the same participant, the participant will be counted only once for that preferred term using the most severe and most related occurrence for the summaries by severity and causality.

The causality and severity of all adverse events will be assessed by the investigator.

The number and percentage of participants reporting TEAEs that are included in the PDSOT term list will be tabulated by study intervention group. The PDSOT term list will be included in the SAP.

AGN-151586

Summary tables will be provided for participants with TESAEs and participants with TEAEs leading to discontinuation if 5 or more participants reported such events. Listings of all adverse events, SAEs, and adverse events leading to discontinuation by participant will be presented.

The definitions of an adverse event and SAE can be found in Appendix 3.

9.4.2.2. Clinical Laboratory Assessments

Descriptive statistics for clinical laboratory values (in SI units) at baseline (screening) and changes from baseline at each assessment will be presented by study intervention for each clinical laboratory assessment.

The criteria for PCS laboratory values will be detailed in the SAP. The number and percentage of participants who have PCS postbaseline clinical laboratory values will be tabulated by study intervention at each assessment. The percentages will be calculated relative to the number of participants who have available non-PCS baseline values and at least 1 postbaseline assessment. The numerator will be the total number of participants with at least 1 PCS postbaseline value. A supportive listing of participants with PCS postbaseline values will be provided for the safety population.

9.4.2.3. Vital Signs

Descriptive statistics for vital signs (systolic and diastolic blood pressure, pulse rate, respiration rate, body temperature) at baseline prior to receiving study intervention (or screening value just prior to baseline if baseline values are not available) and changes from baseline at each assessment will be presented by study intervention.

The criteria for PCS vital signs will be detailed in the SAP. The number and percentage of participants who have PCS postbaseline vital signs will be tabulated by study intervention at each assessment. The percentages will be calculated relative to the number of participants who have available non-PCS baseline values and at least 1 postbaseline assessment. The numerator will be the total number of participants with at least 1 PCS postbaseline value. A supportive listing of participants with PCS postbaseline values will be provided for the safety population.

9.4.2.4. Electrocardiograms

Electrocardiogram evaluations by investigators are captured in the eCRF and are classified into 3 categories: normal, abnormal, or not evaluable. These data will be summarized by study intervention group as the number and percent of participants in each category at each visit. Data listings which include ECG basic parameters and any ECG abnormalities will be produced.

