5.2. Exclusion Criteria

Participants are excluded from the study if any of the following criteria apply:

_	
1.	Medical Conditions
1.01	Any condition that precludes a participant's ability to comply with study requirements, including completion of the study visits or inability to read, understand, and/or self-assess GL severity using the FWS
1.02	Known immunization or hypersensitivity to any botulinum neurotoxin serotype
1.03	Known allergy or sensitivity to any of the components of the study interventions or any materials used in the study procedures
1.04	Any medical condition that may put the participant at increased risk with exposure to AGN-151586, including diagnosed myasthenia gravis, Eaton-Lambert syndrome, amyotrophic lateral sclerosis, or any other condition that might interfere with neuromuscular function
1.05	Any history of significant cardiovascular disease, family history of long QT syndrome, or a clinically significant ECG abnormality at the Screening Visit
1.06	Marked facial asymmetry, dermatochalasis, deep dermal scarring, excessively thick sebaceous skin, or the inability to substantially lessen facial lines even by physically spreading them apart, as determined by the investigator
1.07	Any brow or eyelid ptosis, as determined by the investigator
1.08	Infection or skin disorder at the injection sites
1.09	History of facial nerve palsy
1.10	Any uncontrolled systemic disease
1.11	Any medical condition that, in the opinion of the investigator, puts the participant at undue safety risk
1.12	History of alcohol or drug abuse within 3 months of randomization based on the investigator's judgment
1.13	Anticipated need for treatment with botulinum neurotoxin of any serotype for any reason during the study (other than study intervention)
1.14	Anticipated need for surgery or overnight hospitalization during the study

AGN-151586

2.	Prior/Concomitant Therapy
2.01	Reported use of any botulinum neurotoxin of any serotype for aesthetic treatment within the last 6 months prior to screening and for therapeutic treatment within the last 12 months prior to screening.
2.02	Any of the following procedures or treatments occurring in the specified period before randomization (Day 1):
	3 months : any facial nonablative resurfacing laser, light or ultrasound treatment, microdermabrasion, monopolar radiofrequency, or superficial peels

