8.2.5. Electrocardiograms

- All participants will undergo conventional 12-lead ECG using standardized equipment and electrode placement at the visits outlined in the SoA. Participants are to be in a semirecumbent position for at least 10 minutes prior to starting the tracing. During screening, a 12-lead ECG trace will be taken to assess entry eligibility.
- A qualified third-party vendor will read the ECGs and report the findings as normal, abnormal, or unable to evaluate.
- For screening ECGs, prespecified significant abnormal findings will be flagged as exclusion alerts, and a third-party vendor will generate an exclusion alert for the site and the sponsor. Exclusion alerts are considered exclusionary for study eligibility (see Exclusion Criterion 1.05 in Section 5.2 which excludes any participant with a 'clinically significant ECG abnormality at the Screening Visit'). For all subsequent ECGs, a qualified third-party vendor will also report the appearance of any new, prespecified significant abnormal findings and generate a protocol alert for the site and the sponsor.
- The cardiologists will be blinded to participant study intervention assignments. If the ECG finding is abnormal, they will specify the abnormality or give a diagnosis, whenever it is possible. Electrocardiogram reports will be provided to the investigator and the sponsor via a secure portal within 24 hours of screening and within 72 hours for all other visits.
- Before study intervention, if the ECG finding is clinically significant, it must be captured in the medical history eCRF. After study intervention, if the pre-existing finding becomes worse and is clinically significant or the new ECG finding is clinically significant, it must be captured as an adverse event in the adverse event eCRF. Hard copies of the ECG tracings will be kept in the study files at the investigator's site.
- The ECG will be assessed for the following: heart rate, QRS duration, QT interval, QTcB interval, QTcF interval, ST segment, RR interval, PR interval, and qualitative results.

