#### **5.5.5.      *Electrocardiogram***

Electrocardiogram (ECG) evaluations by investigators are captured in the eCRF and are classified into 3 categories: normal, abnormal, or not evaluable. These data will be summarized by study intervention group as change from baseline for each parameter, as well as the number and percent of participants in each category for PCS. Data listings which include ECG basic parameters and any ECG abnormalities will be produced.

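### The normal/abnormal ECG summary is not tied to the screening ECG, so new abnormalities not judged clinically significant cannot be told apart from stable pre-existing ones.

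*Protocol*

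**What the plan says.** **Category summary, protocol.** Section 9.4.2.4 uses three categories (normal, abnormal, not evaluable): "These data will be summarized by study intervention group as the number and percent of participants in each category at each visit". It adds listings: "Data listings which include ECG basic parameters and any ECG abnormalities will be produced".

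**Category summary, SAP.** Section 5.5.5 has two parts. The numeric part is "These data will be summarized by study intervention group as change from baseline for each parameter". The categorical part is "the number and percent of participants in each category for PCS". The by-visit phrase of the protocol is not repeated, and no denominator rule is given.

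**Laboratory values and vital signs.** Protocol 9.4.2.2 ties the PCS percentage to baseline: "The percentages will be calculated relative to the number of participants who have available non-PCS baseline values and at least 1 postbaseline assessment". Protocol 9.4.2.3 and SAP 5.5.3 and 5.5.4 use the same denominator.

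**Who enters.** Exclusion 1.05 includes "a clinically significant ECG abnormality at the Screening Visit". A reading that is abnormal but not clinically significant is not excluded by that criterion.

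**After dosing.** ECGs are scheduled on Day 2, Day 3, Day 7 and at exit. Under protocol 8.2.5 the vendor will "report the appearance of any new, prespecified significant abnormal findings", with an alert to the site and sponsor. The same section has new or worsened findings recorded as adverse events when they are clinically significant.

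**The concern.** A participant whose screening ECG is read as abnormal but not significant can be enrolled. If nothing changes, that participant is counted as abnormal at up to four post-dose ECGs. A participant who was normal at screening and becomes abnormal after dosing adds to the same count. The planned category display does not separate the two.

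By-visit counts also never give the number of participants with any new abnormal reading during follow-up. The same participant may be abnormal at several visits, and different participants may be abnormal at different visits.

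With about 30 active and 10 placebo participants per cohort, a chance imbalance in pre-existing abnormalities can create or mask a difference between groups. At stake is how informative one descriptive safety display is in a dose-escalation study. The efficacy analysis and the adverse event tables are not affected.

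**Working it through.** **1. What each ECG summary can show**

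| Type of post-dose ECG change | Where it appears | Linked to baseline? |
|---|---|---|
| Numeric parameters (intervals, rate) | SAP 5.5.5, change from baseline | Yes. SAP 5.1 takes the last pre-dose value. The schedule shows no Day 1 ECG, so this is the screening tracing |
| New or worsened, clinically significant | Adverse event (protocol 8.2.5), then the TEAE tables (protocol 9.4.2.1, SAP Table 5-1) | Yes, counted per participant |
| New abnormal reading, not judged clinically significant | Category counts and listings | No |

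Only the third row is uncovered.

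**2. The plan's nearest figure**

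Neither document gives a figure for ECG categories. The closest safety figure is protocol 9.2: about a 60% chance of seeing an adverse event of 3% incidence in 30 participants. It reproduces: 1 − 0.97^30 = 0.599.

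**3. How carried-over and new readings mix**

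Assume that a fraction b of participants has a stable abnormal reading at screening, and that 10% of those normal at screening become abnormal. Both are assumptions. Among 30 active participants, the expected number abnormal is 30b + 30(1 − b) × 0.10.

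| b | Carried over | New | Total abnormal | New as share of total |
|---|---|---|---|---|
| 0% | 0 | 3.0 | 3.0 | 100% |
| 10% | 3.0 | 2.7 | 5.7 | 47% |
| 20% | 6.0 | 2.4 | 8.4 | 29% |
| 40% | 12.0 | 1.8 | 13.8 | 13% |

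Restricted to participants normal at screening, the display would show 2.7/27, 2.4/24 and 1.8/18 for the last three rows. Each is 10%, the rate that was assumed. At b = 0 the two displays agree.

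**4. Chance imbalance with no drug effect**

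Inputs: 30 active and 10 placebo (protocol 9.2), with the same assumed prevalence p in both groups. The standard error of the difference is √[p(1 − p)(1/30 + 1/10)]. The probability of an absolute gap of at least 20 points is the exact sum over two independent binomials.

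| p | Standard error (points) | P(gap ≥ 20 points) |
|---|---|---|
| 5% | 8.0 | 2.9% |
| 10% | 11.0 | 8.4% |
| 20% | 14.6 | 20.9% |

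Worked line for 20%: 0.20 × 0.80 × 0.1333 = 0.0213, whose square root is 0.146. The probabilities cover both directions. At 20% prevalence, 9.9% is active higher and 20.9 − 9.9 = 11.0% is placebo higher.

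For comparison, a count limited to new readings at a 3% rate, with all 30 and 10 participants in the denominator, has a standard error of 6.2 points and a 1.6% chance of such a gap. Restricting to participants normal at screening makes these denominators somewhat smaller.

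**The case against.** The strongest case against the point is that ECG data are already compared with baseline where it matters most. The primary safety endpoint is worded as change from baseline in ECG parameters, and SAP 5.5.5 delivers that. Clinically significant new findings reach the TEAE tables, which count each participant once per preferred term and do not count stable pre-existing findings. All of this stands, and it limits the point to the third row of the first table.

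Three further arguments have some weight:

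- **Screening counts may be shown.** If the by-visit display includes the Screening Visit, a reader can see each group's pre-dose prevalence. That reveals an imbalance, but it does not identify who changed.
- **Healthy population.** Besides exclusion 1.05, inclusion 6.01 requires good health with ECG among the criteria. Prevalence may be low, and at 5% the chance of a 20-point gap is only about 3%.
- **Unseen text.** Part of the SAP table list is redacted, and table specifications are in a separate document. A shift table or ECG PCS criteria may exist there. The visible SAP wording on categories for PCS is unclear, so it would be wrong to assert that ECG PCS criteria are missing from the plan.

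A reader might infer more: that ECG results have no link to baseline at all, that a primary safety measure is compromised, or that pre-existing abnormalities will swamp new ones. The documents do not support these readings. The named measure is change in parameters, and no abnormality rate is given from which swamping could be shown. A power comparison would not help either, because no test on ECG categories is planned.

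**Conclusion.** The point holds in a limited form. As described in both documents, the qualitative ECG summary lacks the baseline restriction that the same plan applies to laboratory and vital-sign PCS values. As a result, new abnormal readings not judged clinically significant are mixed with stable screening abnormalities, and no participant-level count of new abnormal readings is stated.

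The size cannot be determined from the documents. The 5% to 20% prevalence range, with its 3% to 21% chance of a 20-point gap, is an assumption, as is the 10% new-onset rate in the illustration. The supportable statement is that pre-existing abnormalities can obscure new ones in this display.

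The two documents also describe the ECG summary differently, while SAP 6.2 declares only one change to the protocol-planned analyses, which concerns TEAEs. That difference should be resolved in any case. Nothing here invalidates the trial. It is a worthwhile improvement to a descriptive safety table.

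**What to change.** In protocol 9.4.2.4 and SAP 5.5.5:

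1. Add a shift table from the screening ECG category to the category at each post-dose visit and to the worst post-dose category.
2. Add the number and percent of participants with at least one abnormal post-dose ECG. The denominator is participants with a normal screening ECG and at least one post-dose ECG, which follows the rule already used for laboratory and vital-sign PCS values.
3. Show both by dose, own-cohort placebo and pooled placebo.
4. Keep the by-visit counts and the change-from-baseline summaries.
5. Reconcile the wording of 9.4.2.4 with SAP 5.5.5, including what the categories for PCS are, and record any difference in SAP 6.2. State also whose reading supplies the category: 8.2.5 describes a vendor reading, while 9.4.2.4 and SAP 5.5.5 refer to evaluations by investigators.

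The cost is a wording change and a small addition to the tables. The screening and post-dose readings are already collected.

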9.4.3. Other Analyses

9.4.3.1. Immunogenicity Analyses

Immunogenicity results, manifested as the presence of binding antibodies, and neutralizing antibodies if a validated assay becomes available, to AGN-151586, will be summarized in a table

Protocol 2034-201-008 Amd 1

AGN-151586

and reported for each sampling timepoint. Additional immunogenicity exploratory analyses may be performed; results will be summarized in the clinical study report or in a separate report.

9.5. Interim Analyses

No interim analysis is planned.

10. Supporting Documentation and Operational Considerations

10.1. Appendix 1: Regulatory, Ethical, and Study Oversight Considerations

10.1.1. Regulatory and Ethical Considerations

- This study will be conducted in accordance with the protocol and with the following:
 - Consensus ethical principles derived from international guidelines including the Declaration of Helsinki and Council for International Organizations of Medical Sciences (CIOMS) International Ethical Guidelines
 - o Applicable ICH/ISO Good Clinical Practice (GCP) guidelines
 - o Applicable laws and regulations
- The protocol, protocol amendments, ICF, investigator's brochure, and other relevant documents (eg, advertisements) must be submitted to an IRB/IEC by the investigator and reviewed and approved by the IRB/IEC before the study is initiated.
- Any amendments to the protocol will require IRB/IEC approval before implementation of changes made to the study design, except for changes necessary to eliminate an immediate hazard to study participants.
- The investigator will be responsible for the following:
 - Providing written summaries of the status of the study to the IRB/IEC annually or more frequently in accordance with the requirements, policies, and procedures established by the IRB/IEC
 - Notifying the IRB/IEC of SAEs or other significant safety findings as required by IRB/IEC procedures
 - o Providing oversight of the overall conduct of the study at the site and adherence to requirements of applicable local regulations, for example 21 CFR, ICH guidelines, the IRB/IEC, and European regulation 536/2014 for clinical studies (if applicable)

10.1.2. Financial Disclosure

Investigators and subinvestigators will provide the sponsor with sufficient, accurate financial information as requested to allow the sponsor to submit complete and accurate financial certification or disclosure statements to the appropriate regulatory authorities. Investigators are responsible for providing information on financial interests during the course of the study and for 1 year after completion of the study.

10.1.3. Informed Consent Process

• The investigator or his/her representative will explain the nature of the study to the participant or his/her legally authorized representative and answer all questions regarding the study.

AGN-151586

- Participants must be informed that their participation is voluntary. Participants will be required to sign a statement of informed consent that meets the requirements of 21 CFR 50, local regulations, ICH guidelines, HIPAA requirements, where applicable, and the IRB/IEC or study center.
- The medical record must include a statement that written informed consent was obtained before the participant was enrolled in the study and the date the written consent was obtained. The authorized person obtaining the informed consent must also sign the ICF.
- Participants must be reconsented to the most current version of the ICF(s) during their participation in the study.
- A copy of the ICF(s) must be provided to the participant or the participant's legally authorized representative.
- Participants who are rescreened are not required to sign a new ICF if rescreening occurs within 30 days of first signing the ICF.

